	
“Is the participant eligible for the study based on the screening?”
 
Under this question are self-reported age, presence of spinal cord injury, and current pregnancy from F02 Form completed by the potential participant. Eligibility is determined by three criteria: 1) between the ages of 18 to 65, 2) presence of spinal cord injury, and 3) not currently pregnant.
 
Go to REDCap and call the potential participant using the phone number stored under the F01 Form. Contact him/her at preferred contact time. Record the phone call/ attempt using the Call Log in REDCap.
 
Group 1: Ineligible, Yes for medical clearance
 
** A total of 3 call attempts should be made with each being at least 3 days apart if the potential participant cannot be reached.
 
** If the potential participant cannot be reached this time, please make sure to exit the Medical Clearance Form by clicking the Cancel button at the end of the form, which will ensure the form status remains as No Color (Incomplete or Red status indicates a person is ineligible).
 
(1) Eligibility
 
If the potential participant is outside of the age range, confirm the reported Date of Birth is accurate. If the Date of Birth is inaccurate, correct the information under F02 Form. Once the potential participant is determined as eligible, check Yes and obtain physician contact information.
 
If the potential participant does not respond 3 days after the 3rd call attempt, please assume the reported Date of Birth is accurate. Check No and Save and Exit Form as Incomplete. No further action is required at this point.
 
(2) Physical, mailing address
 
If the potential participant is determined as eligible, check and confirm the potential participant's mailing address for future equipment shipping. If change is needed, revise the address fields under the F02 Form.
 
Indicate whether or not the participant's mailing address has confirmed (yes/no). This question is located in the F02 Form as below:
 
“Participant’s mailing address has been confirmed during the process of obtaining physician’s contact information”
 
(3) Obtain physician contact Information (see Appendix I for script to obtain physician contact information)
 
Record the physician contact information under the Medical Clearance Form in REDCap.
 
Group 2: Eligible, Yes for medical clearance
 
** A total of 3 phone calls should be made with each being at least 3 days apart if the potential participant cannot be reached.

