		
Go to REDCap and call the participant using the phone number stored under F02 Form. If the participant responds to the phone call, inform him/her that you sent the Packet 1 again and ask to complete it within the next 7 days.
 
If the participant does not respond to the phone call, leave a voice message and email to inform him/her that you sent the Packet 1 again and ask to complete it within the next 7 days.
 
Record the call attempt using the call log in REDCap.
 
For Partially Completed Packet (Follow up with 2 contact attempts)
 
Go to REDCap and call the participant using the phone number stored under F02 Form.
 
If the participant responds to the phone call, inform him/her that the questionnaire packet he/she completed has missing responses and ask if he/she is ok to provide you the responses over phone. If he/she agrees, open Packet 1 the participant partially completed in REDCap and click Edit Response on top of the packet. Go through the items with missing responses with the participants and enter responses obtained from the participants. Save and Exit the Form when finished.
 
*In the case of a participant making the initial contact via email about not being able to re-open the packet again, please contact PI to obtain a direct link to the packet and send to the participant. Please consider this email contact as the 1st contact attempt.
 
If the participant does not respond to the phone call, leave a voice message and email to inform him/her that you are contacting him/her about missing responses in the questionnaire packet and will call again within the next 7 days.
 
Call again within the next 7 days to complete the 2nd contact attempt.
 
Record the call attempt(s) using the call log in REDCap.

	2	
If the potential participant completes the Packet 1 within 7 days, continue with Step 5

	3	
If the potential participant did not complete the Packet 1 within 7 days after the phone call (22 days from the initial Packet 1), an email notification, Incomplete Packet 1, will be sent out to the study email. Continue with Step 4.

	4	
Under the Lost to Contact/Withdrawn Form in REDCap, mark the person as Lost to Contact and indicate the date when the lost to contact was determined during the study period (Post screening & Before baseline). No further action is required.

Perform Randomization		

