12	
The auto invitation of the Packet 2 or 2-1 (post-intervention), Packet 3 (12-week), and Packet 4 (16-week) are set to send up to 3 times, every 3 days:
 
 The initial Packet 2 or 2-1 is sent 58 days after participant completed randomization. When the initial Packet 1 is not completed by the participant within 3 days (3 days from the first Packet 1), a second Packet 2 or 2-1 will be sent automatically from REDCap. No action is required. When the second Packet 2 or 2-1 is not completed by the participant after 3 days (6 days from the initial Packet 1), a third Packet 2 or 2-1 will be sent automatically from REDCap. 
If the participant completes Packet 2 or 2-1 before the third invitation, an email notification, Complete Post-Intervention Event, will be sent to the study email.
 
If the participant did not complete Packet 2 or 2-1 and the third invitation is sent, an email notification, Incomplete Packet 2 or 2-1, will be sent to the study email. Continue with Step 13.
 
*If the participant has Packet 2 or 2-1 partially completed (form status shown as Partial Survey Response, orange color), continue with the sub-section (For Partially Completed Packet) of Step 13.

----	--

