	
Go to REDCap and call the participant using the phone number stored under F02 Form. If the participant responds to the phone call, inform him/her that you sent the Packet 2 or 2-1 again and ask to complete it within the next 3 days. Continue with Step 15.
 
If the participant does not respond to the phone call, leave a voice message and email to inform him/her that you sent the Packet 2 or 2-1 again and ask to complete it within the next 3 days. Continue with Step 14.
 
Record the call attempt using the call log in REDCap.
 
For Partially Completed Packet (Follow up with 2 contact attempts)
 
Go to REDCap and call the participant using the phone number stored under F02 Form.
 
If the participant responds to the phone call, inform him/her that the questionnaire packet he/she completed has missing responses and ask if he/she is ok to provide you the responses over phone. If he/she agrees, open Packet 2 or 2-1 the participant partially completed in REDCap and click Edit Response on top of the packet. Go through the items with missing responses with the participants and enter responses obtained from the participants. Save and Exit the Form when finished.
 
*In the case of a participant making the initial contact via email about not being able to re-open the packet again, please contact PI to obtain a direct link to the packet and send to the participant. Please consider this email contact as the 1st contact attempt.
 
If the participant does not respond to the phone call, leave a voice message and email to inform him/her that you are contacting him/her about missing responses in the questionnaire packet and will call again within the next 3 days.
 
Call again within the next 3 days to complete the 2nd contact attempt.
 
Record the call attempt(s) using the call log in REDCap.

14	
If the potential participant did not complete the Packet 2 or 2-1 within 3 days after the phone call (10 days from the initial Packet 2 or 2-1), an email notification, Incomplete Packet 2 or 2-1, will be sent out to the study email.
 
Under the Lost to Contact/Withdrawn Form in REDCap, mark the person as Lost to Contact and indicate the date when the lost to contact was determined during the study period (Post 8-week intervention). Continue with Step 15.

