If the participant did not respond to the phone call, please make 2 additional call attempts, with each 3 days apart. Enter the **date** when the 2nd or 3rd call attempt is made under the *Post-Intervention Participant Interview* form in REDCap.

If participant answers the call, follow **Action #1-3** to complete the interview process.

If participant still did not respond to the 3rd call attempt, please **Save and Exit** the form as **Incomplete**. This action will remove the participant from the *Participants to be Invited for Interview* report.

Statistical Analysis for Pilot Usability Phase

Descriptive statistics for participant demographics, feasibility, usability, acceptability metrics, and preliminary study outcomes were computed as mean \pm SD or median (minimum, maximum) for continuous variables and percentage (*n*) for categorical variables. A sample size of 36 was determined based on recommendations for feasibility studies assessing feasibility, usability, and acceptability³⁸.

Preliminary data (LTPAQ-SCI and PROMIS) collected at baseline and Week 8 were analyzed, with Week 8 as the primary endpoint. Prior to analyses, data were examined for errors, missingness, and normality. Three participants (*n*=1 in SET, *n*=2 in AC) were identified as outliers for all LTPAQ-SCI categories (Studentized residual > 3.0 and high leverage on predictors of interest). These data were presumed to result from measurement errors and were excluded from all LTPAQ-SCI analyses.

Given the exploratory nature of this interim analysis and the small sample size, we focused on effect sizes for the preliminary study outcomes. Linear mixed models were used to assess within- and between-group effects using an intent-to-treat approach and included fixed effects for Time (Week 8 vs baseline) and Intervention Arm, a random effect for participant, and a Time x Intervention Arm interaction. Estimates were derived from least-square mean differences, with bootstrap confidence intervals (CIs) calculated at the 95%, 85%, and 75%. All LTPAQ-SCI measures were square-root transformed for analysis to meet normality assumption.

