Effect sizes were calculated using Hedge's *g*, which is based on the pooled SD and corrected for small samples. Interpretations of *g* were: $g < 0.2$ =very small; $0.2 \leq g < 0.5$ =small; $0.5 \leq g < 0.8$ =medium; $g \geq 0.8$ =large³⁹. Rank-biserial correlation index (*r_{rb}*) were also used with the following interpretations: $0.05 \leq r_{rb} < 0.1$ =very small; $0.1 \leq r_{rb} < 0.2$ =small; $0.2 \leq r_{rb} < 0.3$ =medium; $0.3 \leq r_{rb} < 0.4$ =large; $r_{rb} \geq 0.4$ =very large⁴⁰.

Analyses were performed using R version 4.3.3 (R Core Team, 2024)⁴¹ and the following packages: tidyverse v2.0.0⁴², DescTools v0.99.54⁴³, gtsummary v1.72⁴⁴, lme4 v1.1-35.3⁴⁵, lmerTest v3.1-3⁴⁶, emmeans v1.11.0⁴⁷, effectsize v0.8.7⁴⁸, broom.mixed v0.2.9.6⁴⁹, ggplot2 v3.5.2⁵⁰, and ggpubr v0.6.0⁵¹.

Statistical Analysis for Feasibility Phase

Data collected at baseline and Week 8 were included in the current analyses, with Week 8 evaluated as the primary endpoint. The primary outcome for this study was change in physical activity (LTPAQ-SCI), whereas changes in physical, mental and social health (NIH PROMIS) were evaluated as secondary outcomes. All data were examined prior to analysis for errors, missingness, and normality. For LTPAQ-SCI measures, five participants ($n=3$ in Arm 1 and $n=2$ in Arm 2) had unusually high scores for mild, moderate, and total LTPA, and were identified as model outliers for these outcomes (Studentized residual > 3.0 and high leverage). Ultimately, these participants were excluded from analyses of the primary outcome due to the high likelihood of data entry errors during data collection.

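### Packet follow-up queries only missing answers; no described step asks a participant to confirm or correct an implausible LTPAQ-SCI value before it is excluded at analysis

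*Combined protocol and SAP*

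**What the plan says.** **Collection.** The Packet 1 procedure (Steps 1 to 4) and the post-intervention procedure (Steps 12 to 14) have two triggers for follow-up. One is that the packet has not been completed. The other is that it is partly completed ("form status shown as Partial Survey Response, orange color"). Under the sub-section for partially completed packets, staff call to "inform him/her that the questionnaire packet he/she completed has missing responses and ask if he/she is ok to provide you the responses over phone". They then open the record for editing: "Go through the items with missing responses with the participants and enter responses obtained from the participants". Step 15 extends the post-intervention steps to Packets 3 and 4. A completed Packet 1 goes on to Step 5, randomization. A completed Packet 2 or 2-1 produces a notification email.

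**Analysis.** The Pilot Usability Phase section says "Prior to analyses, data were examined for errors, missingness, and normality", and the Feasibility Phase section has an equivalent sentence. In the pilot, three participants (1 SET, 2 AC) were flagged on LTPAQ-SCI by Studentized residual and leverage: "These data were presumed to result from measurement errors and were excluded from all LTPAQ-SCI analyses". In the Feasibility Phase, where LTPAQ-SCI change is the primary outcome, five participants (3 in Arm 1, 2 in Arm 2) with unusually high scores were flagged in the same way and "excluded from analyses of the primary outcome due to the high likelihood of data entry errors during data collection".

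**The concern.** The plan's own explanation for losing primary-outcome data places the fault at data collection, yet the collection steps as described look only for blanks. A value that is present but implausible passes through them and is first examined when the analysis is prepared. Neither analysis section reports a query to the participant or a check against source. The analyst then has only a model residual on which to judge whether a high score is a mistake or real activity, and the words chosen (presumed, high likelihood) show that the cause was inferred.

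At stake are randomised participants dropping out of the comparison on the primary outcome, under an analysis described as intent-to-treat, for a reason nobody confirmed. A query before the data are closed would help in either case: an error could be corrected, and a true high value could be confirmed and kept.

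**Working it through.** The point is mainly procedural, so the first check sets the steps side by side.

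| Stage | What triggers action | What is asked |
|---|---|---|
| Screening, Steps 8 and 11 | Age outside the eligible range | Staff call, up to three times, to "confirm the reported Date of Birth is accurate" |
| Packet 1, Steps 1 to 4 | Not completed, or partial | Complete it, or supply the blanks |
| Packet 2 or 2-1, Steps 12 to 14 | Not completed, or partial | Complete it, or supply the blanks |
| Packets 3 and 4, Step 15 | As for Packet 2 | As for Packet 2 |
| Before analysis, both phases | Examination for errors; residual and leverage flags | No query to the participant described |

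The team already goes back to people about a doubtful reported value at screening. It does not do so, in the text available, for an outcome value.

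**Counts by arm.** Pilot: 1 + 2 = 3. Feasibility Phase: 3 + 2 = 5. Both agree with the stated totals.

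**Share of participants.**
- Pilot, assuming all 36 otherwise had analysable LTPAQ-SCI data: 3/36 = 8.3%.
- Feasibility Phase, size not stated: 5/36 = 13.9%, 5/60 = 8.3%, 5/100 = 5.0%, 5/200 = 2.5%.

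**Illustrative cost in precision.** Assume 1:1 allocation, an unchanged SD, two-sided alpha of 0.05 (the plan gives 0.05 without sidedness) and a design with exactly 80% power before exclusions. None of these except the 0.05 is stated in the plan.
- SE ratio = sqrt[(1/m1 + 1/m2) / (1/n1 + 1/n2)], where n and m are the arm sizes before and after exclusion.
- Power after exclusion = Φ[(1.960 + 0.842) / SE ratio − 1.960].
- Pilot, 18/18 falling to 17/16: SE ratio = sqrt[(1/17 + 1/16) / (2/18)] = 1.04; power about 76%.
- Feasibility Phase, N = 36 (18/18 to 15/16): SE ratio 1.08; power about 74%.
- N = 60 (30/30 to 27/28): 1.04; about 76%.
- N = 100 (50/50 to 47/48): 1.03; about 78%.
- N = 200 (100/100 to 97/98): 1.01; about 79%.

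These figures hold the SD fixed. Removing extreme values usually lowers the residual SD, so the actual standard error could have fallen. They show only what losing that number of participants costs in sample size; they do not measure harm done.

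**The case against.** **Silence is not proof.** The step lists are a coordinator's checklist. Field validation belongs to the survey build and need not appear there, and some text just before the Packet 1 steps was not available for this review. This stands. The finding is that the available text describes no plausibility query; a reader should not infer that the packets accept any value whatever. If limits exist, they did not prevent these exclusions.

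**A repeated failure?** A reader might infer that the pilot exposed the problem and the trial then lost five further participants to it. The documents do not support that. The pilot section calls its analysis interim and does not say whether its participants also enter the Feasibility Phase analysis, so the five may include some or all of the three. The stated reasons also differ: measurement error in the pilot, entry error later. In the pilot LTPAQ-SCI was a preliminary outcome; it is named primary only in the Feasibility Phase section.

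**Would a query have worked?** Unknown. The exclusions came from model-based flags, which a range rule may not reproduce. Some queries go unanswered, some errors would be wrongly confirmed, and asking about high values only corrects in one direction. Staff also enter answers by phone, so a prompt seen only by participants could miss the source. These objections shape the fix. They do not remove the gap, because a query still gives a basis other than a residual for the decision.

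**Instrument details.** The documents give no recall period, item format or units for LTPAQ-SCI, so the point cannot rest on any of them.

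**Too late.** The analyses are reported in the past tense, so those values cannot now be recovered by a change in procedure. That stands; the change serves any remaining packets and the next phase.

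**Conclusion.** The point holds in limited form. As described, packet follow-up covers non-completion and blanks only. No step asks a participant about an implausible LTPAQ-SCI value, and the examination for errors comes just before analysis. Three pilot participants and five Feasibility Phase participants were excluded for presumed errors: 8.3% of 36 in the pilot if all 36 were otherwise analysable, and 13.9% down to 2.5% in the Feasibility Phase over an assumed 36 to 200.

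It is tempting to read this as eight participants lost who could have been saved. The documents support neither the sum nor the recovery. The most a query could have kept is three in one analysis and five in the other, and the documents do not show whether the values were errors or true activity. The loss of precision is likewise illustrative and rests on an unchanged SD. This is a cheap improvement to data capture that bears on the primary outcome. How the analysis should treat the participants already excluded is a separate question.

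**What to change.** For any remaining packets and for the next phase:

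1. In the REDCap packets, set limits on the LTPAQ-SCI fields that match the instrument's own response format. Add an on-screen prompt asking the respondent to confirm or correct an unusual entry before submitting.
2. Add a REDCap rule, identical in both arms, with a threshold fixed in advance and without reference to arm. It should list packets with implausible values, whether submitted by the participant or entered by staff, and the participant should be queried within the existing contact window.
3. Store the original value, the corrected value and a confirmation flag. Retain confirmed values in the analysis.
4. If field limits or queries already exist but are not described, state them.

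**Cost.** Field settings, one report and one message template, using call logs and packet links the team already has. The downsides are an extra prompt or contact for some participants, a possible influence of the prompt on self-report, and some queries left unanswered. Applying the rule identically in both arms limits the risk that it affects one arm more than the other.

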Descriptive statistics were computed as mean (SD) and median (min, max) for continuous variables, and n (%) for categorical variables. Characteristics for the overall sample and by intervention arm were reported for 1) demographics, spinal cord injury, health, and lifestyle at baseline; and 2) primary and secondary outcomes at baseline and Week 8. Additionally, results for exercise enjoyment (PACES) were reported for Arm 2 participants at Week 8. Group differences in descriptive characteristics were assessed with the Wilcoxon rank-sum test (non-parametric two-sample t-test), Pearson's Chi-squared test, or Fisher's exact test as appropriate. Mixed models were used to evaluate within- and between-group effects on the primary and secondary outcomes, with analyses conducted using an intent-to-treat approach. Models included time (baseline vs Week 8) and intervention (Arm 1 vs Arm 2) as fixed effects, participant as a random effect, and an interaction term for time x intervention arm. Within- and between-group estimates were derived from the interaction term and are reported as the difference in least-square means (95% CI). For these analyses, all LTPAQ-SCI measures were square-root transformed to ensure that the normality assumption was met, and confidence intervals were estimated via bootstrap methods. All analyses were performed using R version 4.5.0 (R Development Core Team, 2025) (3) and the following packages: tidyverse (4), doBy (5), broom.mixed (6), DescTools (7), gtsummary (8), lme4 (9), lmerTest (10), emmeans (11), effectsize (12), psych (13), and ggplot2 (14). Significance was set at $\alpha=0.05$ for all analyses.

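### High activity scores cannot create high leverage in the time-by-arm model, so the stated outlier criterion cannot support the LTPAQ-SCI exclusions

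*Combined protocol and SAP*

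**What the plan says.** Under Statistical Analysis for Feasibility Phase, the plan reports that "five participants ($n=3$ in Arm 1 and $n=2$ in Arm 2) had unusually high scores for mild, moderate, and total LTPA" and that they were "identified as model outliers for these outcomes (Studentized residual > 3.0 and high leverage", a two-part diagnostic. It concludes that "these participants were excluded from analyses of the primary outcome due to the high likelihood of data entry errors during data collection".

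Under Statistical Analysis for Pilot Usability Phase, three participants (one SET, two AC) are left out of every LTPAQ-SCI analysis on the criterion "Studentized residual > 3.0 and high leverage on predictors of interest". Measurement error is presumed.

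The feasibility model is described as follows: "Models included time (baseline vs Week 8) and intervention (Arm 1 vs Arm 2) as fixed effects, participant as a random effect", plus "an interaction term for time x intervention arm". The pilot model has the same structure. Neither section lists a covariate or a continuous predictor. Neither gives a leverage cutoff, names a separate screening model, or says whether the screen was run on the raw or the square-root scale.

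**The concern.** Leverage measures how unusual an observation's predictor values are. Here the predictors are two visits and two arms, and everyone in an arm at a visit shares the same values. A very high activity score can give a large residual. It cannot give high leverage on time or arm. The second half of the criterion therefore adds no evidence against the people it is said to identify.

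What is at stake is who is in the primary-outcome dataset. The exclusions followed inspection of outcome data and are uneven by arm (3 and 2 in the feasibility phase, 1 and 2 in the pilot). No check against a source is described. The diagnostic is the only quantitative support offered, and a second analyst cannot reproduce it from the text. This is separate from whether such exclusions fit the intent-to-treat label: changing the label would leave the criterion as it is.

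**Working it through.** **Inputs from the documents.** The fixed effects are two-level time, two-level arm and their interaction, so p = 4. There is a random participant effect. On visits: "Data collected at baseline and Week 8 were included in the current analyses". The only sample size given is 36, for the pilot.

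**Assumptions.** The documents give no arm sizes, dropout or intra-class correlation (ICC). I use 18 per arm (36/2) and 50 per arm, and ICC 0.2, 0.5 and 0.8. The five exclusions themselves cannot be reproduced, because no participant data are given.

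**Step 1: fixed-effect leverage.** Time, arm and their interaction fit four cell means, so h = 1/(number in the cell). The outcome does not enter the formula.

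- 18 per arm, complete: N = 72 observations and h = 1/18 = 0.0556 for all of them. The mean is p/N = 4/72 = 0.0556, and the conventional flag is 2p/N = 8/72 = 0.111.
- 18 per arm, 4 per arm missing Week 8: h = 0.0556 at baseline and 1/14 = 0.0714 at Week 8. The flag is 8/64 = 0.125.
- 50 per arm, 10 per arm missing Week 8: h = 0.020 at baseline and 0.025 at Week 8. The flag is 8/180 = 0.044.

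Generalised least squares with the random intercept gives the same diagonal values. With n per arm at baseline and m per arm at Week 8, Week 8 leverage passes the flag only if 1/m > 8/(2n + 2m). That means m < n/3, or more than two thirds of Week 8 data missing. Even then the whole cell passes together.

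**Step 2: leverage including the random effect.** Let r = ICC/(1 − ICC).

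- Both visits, complete data: h = 1 − [(1 + r)/(1 + 2r)](1 − 1/n). At n = 18 this is 0.213, 0.370 and 0.475 for ICC 0.2, 0.5 and 0.8, with one common value for everyone. For ICC 0.5: 1 − (2/3)(17/18) = 0.370.
- Baseline only: h = 1 − [1/(1 + r)](1 − 1/n). For ICC 0.5: 1 − (1/2)(17/18) = 0.528.

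With 18 per arm, 4 per arm missing Week 8 and ICC 0.5, both-visit participants have 0.373 at baseline and 0.381 at Week 8, and baseline-only participants have 0.528. The mean is (28 × 0.373 + 8 × 0.528 + 28 × 0.381)/64 = 0.396, and twice the mean is 0.792. So baseline-only people stand out, at 1.33 times the mean, but because a visit is missing and not because of a score. Across ICC 0.2 to 0.8 in this layout the ratio runs from 1.10 (0.244/0.223) to 1.55 (0.811/0.524), always below 2.

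**Step 3: what the joint rule does.** Any cutoff passes or fails all both-visit participants in a cell together. If they pass, the rule is residual > 3.0 alone. If they fail, it selects none of them. In a simulated complete dataset of 50 per arm with five planted gross outliers (3 and 2 by arm), the residual half alone flagged exactly those five. Adding leverage > 2p/N = 8/200 = 0.04 flagged nobody, since every leverage was 0.020.

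**Step 4: a model where leverage would vary.** In the same simulated data, a regression of Week 8 on baseline gave leverages from 0.020 to 0.103, because the baseline score is then a predictor. Neither section describes such a model.

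**The case against.** The strongest reply is that the sections report a judgement made after looking at the data, not a mechanical algorithm. Unusually high scores, the diagnostics and the likelihood of entry error were weighed together. The leverage remark may be redundant beside a residual screen, a loose name for an influence statistic, or taken from an unmentioned Week 8 on baseline screen. Any of these could explain the exclusions, and the documents do not say that the screen used the final mixed model. This stands. It means the exclusions are not shown to be wrong, and it leaves the text needing to say which explanation applies.

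Two stronger readings are tempting but unsupported. First, a reader might infer that an analyst following the text would keep all eight excluded people. No cutoff is stated, so the rule may equally act as residual > 3.0 alone, and the documents do not say whether the excluded people had both visits. Nor is eight a safe count: the pilot analysis is called interim, so its three may be among the five. Second, a reader might want a rate at which error-free skewed data would exceed the residual limit. That depends on distribution and scale, which are not given. It also depends on how many activity categories must be flagged together: the pilot refers to all of them, and the feasibility phase to mild, moderate and total. A rate for one raw-scale outcome would overstate chance flagging, so I give none.

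**Conclusion.** The concern holds in this form: under the only model described, high leverage cannot result from high activity scores, so the stated criterion cannot support the exclusions (three in the pilot, five from the feasibility primary outcome, overlap unstated). The criterion is wrong as written for that model, not merely short of detail. The one escape is that another model or statistic was used and not named.

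Equality of leverage among both-visit participants in a cell is algebra and does not depend on the assumed 18 per arm or ICC 0.5. The specific leverage values do depend on them. The finding that baseline-only participants stay below twice the mean rests on the ranges tried. The effect on the treatment estimate cannot be sized without the data, and nothing here shows that the excluded values were genuine.

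**What to change.** 1. In both sections, strike the high-leverage wording. Name the model, outcome scale, statistic and cutoff actually used to identify the excluded participants, and say whether the pilot and feasibility exclusions overlap.
2. For flagging, use participant-level influence on the square-root-scale model: Cook's distance, or DFBETAS for the time-by-arm term, leaving out one participant at a time. A flag should only trigger a check of the record.
3. Remove a value only if it breaks a fixed limit on the raw answer, set without regard to arm (for example, more hours than a day holds), or if an entry error is confirmed.
4. Report the primary LTPAQ-SCI result with all participants included, beside the result with exclusions.

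The cost is a change of wording, one re-run of the diagnostics and one further fit of the existing model. The downside is that fewer values may qualify for removal. An implausible score that breaks no limit and cannot be confirmed as an error would stay in, and the estimate may be noisier.
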